18.1 Informed Consent Form

18.2 Study Questionnaires

Short FES-I

Now we would like to ask some questions about how concerned you are about the possibility of falling. Please reply thinking about how you usually do the activity. If you currently don't do the activity, please answer to show whether you think you would be concerned about falling IF you did the activity. For each of the following activities, please tick the box which is closest to your own opinion to show how concerned you are that you might fall if you did this activity.

Not at all Somewhat Fairly Very concerned concerned concerned concerned 1 2 3 1 \square 2 *3* \square 4 🗆 1 Getting dressed or undressed 1 \square 2 Taking a bath or shower $2 \square$ *3* \square 4 \square 1 \square 2 \square *3* \square 3 Getting in or out of a chair 4 \square 4 Going up or down stairs 1 \square $2 \square$ *3* \square 4 2 \square 5 Reaching for something above 1 \square *3* \square 4 your head or on the ground 1 \square 2 \square *3* \square 4 🗆 6 Walking up or down a slope 1 \square $2 \square$ *3* \square 4 🗆 Going out to a social event (e.g. religious service, family gathering or club meeting)

Brief Interview for Mental Status (BIMS)

Repetition of Three Words				
Ask resident: "I am going to say three words for you to remember. Please repeat the words after I have said all three. The words are: sock, blue and bed. Now tell me the three words."				
Number of words repeated after first attempt:				
0. None 1. One 2. Two 3. Three				
After the resident's first attempt, repeat the words using cues ("sock, something to wear; blue, a color; bed, a piece of furniture"). You may repeat the words up to two more times.				
Temporal Orientation (orientation to month, year and day)				
Ask resident: "Please tell me what year it is right now."				
Able to report correct year				
0. Missed by > 5 years, or no answer				
1. Missed by 2-5 years				
2. Missed by 1 year				
3. Correct				
Ask resident: "What month are we in right now?"				
Able to report correct month				
0. Missed by > 1 month, or no answer				
1. Missed by 6 days to one month				
2. Accurate within 5 days				
Ask resident: "What day of the week is today?"				
Able to report correct day of the week				
0. Incorrect, or no answer				
1. Correct				
Recall				
Ask resident: "Let's go back to the earlier question. What were the three words that I asked you to repeat?" If unable to remember a word, give cue ("something to wear," "a color," "a piece of furniture") for that word.				
Able to recall "sock" 0. No - could not recall 1. Yes, after cueing ("something to wear") 2. Yes, no c required				
Able to recall "blue" 0. No - could not recall 1. Yes, after cueing ("a color") 2. Yes, no c required				
Able to recall "bed" 0. No - could not recall 1. Yes, after cueing ("a piece of furniture") 2. Yes, no c required				
Summary Score				
Add scores for each question and fill in total score (00-15). Enter 99 if the resident was unable to complete the interview.				

Active Protective Technologies, Inc COP-0001 Version 2

Confidential

1 ABBREVIATIONS

Abbreviation	Definition
AE	Adverse Event
CRF	Case Report Forms
CSR	Clinical Study Report
ED	Emergency Department
EMR	Electronic Medical Record
FDA	United States Food and Drug Administration
GSD	Group Sequential Design
ITT	Intent-To-Treat Population
IPTW	Inverse Probability of Treatment Weighted
NNM	Nearest Neighbor Matching
PP	Per-Protocol Population
PS	Propensity Score
PSM	Propensity Score Matching
PT	Preferred Term
SAE	Serious Adverse Event
SAP	Statistical Analysis Plan
SOC	System Organ Class
SSRE	Sample Size Re-estimation

2 SUMMARY

TITLE	Mitigation of Major Hip Injury due to fall in an At-Risk, Older Adult Population with a Wearable Smart Belt
PREFACE	This Statistical Analysis Plan (SAP) describes the planned analysis and reporting for Active Protective Technologies protocol COP-0001 (Mitigation of Major Hip Injury due to fall in an At-Risk, Older Adult Population with a Wearable Smart Belt). This study is being completed to assess the safety and efficacy of Tango® Belt for the treatment of the Tango Belt as an adjunctive intervention to the standard-of-care (SOC) to mitigate major hip injuries due to falls in an older adult population (65+ years of age) at-risk for fall injury.
	 The following documents were reviewed in preparation of this SAP: Clinical Research Protocol COP-0001 v2.0, issued 18APR2022 Case report forms (CRFs) Casebook Rev 1.0, annotated Rev.01
PURPOSE	The purpose of this SAP is to outline the planned analyses in support of the Clinical Study Report (CSR) for protocol COP-0001. Exploratory analyses not necessarily identified in this SAP may be performed to support the clinical development program. Any post-hoc, or unplanned, analyses not identified in this SAP will be clearly identified in the respective CSR.
STUDY OBJECTIVES	Primary Objective: To assess the performance of the Tango® Belt to mitigate fall-related major hip injuries in an at-risk-of-fall-injury adult population as compared to the standard of care (SOC) only. Secondary Objectives: To assess the performance of the Tango Belt to mitigate falls resulting in: (1) hip fractures, (2) emergency department (ED) visits or (3) hospitalizations.
STUDY DESIGN	Multi-center, comparative, non-significant risk adaptive study with historical controls. After providing informed consent and being screened for eligibility, intervention subjects will be prescribed and provided an appropriately sized Tango Belt. The subject must demonstrate a minimum of 64% adherence to the use of the Tango Belt within 14 days of initiation to fully enroll in the study. Upon demonstration of at least minimum adherence, the subject will be provided the Tango Belt to wear continuously for at least 6 months, except during bathing, device charging, and as deemed by clinical staff.
ENDPOINTS	The study will Investigate the safety and effectiveness of the Tango Belt with the primary and secondary endpoints being taken every 3 months and at the end of the study run time from the electronic medical record. Additionally, ancillary endpoints on adverse events and device performance will be gathered. Primary:

The study's **primary effectiveness endpoint** is the proportion of major hip injuries due to fall in the subjects receiving SOC as compared to subjects receiving SOC plus the Tango Belt.

There is no primary safety endpoint for this study. This is a non-significant risk study. Safety of the device will be determined by analysis of adverse events as an ancillary endpoint.

Secondary:

The study's **secondary endpoints** include the proportion of each of the following:

- Hip fractures due to fall in the subjects receiving SOC as compared to subjects receiving SOC plus the Tango Belt.
- Emergency Department (ED) visits due to fall in the subjects receiving SOC as compared to subjects receiving SOC plus the Tango Belt.
- Hospitalizations due to fall in the subjects receiving SOC as compared to subjects receiving SOC plus the Tango Belt.

Ancillary:

Ancillary endpoints will include:

- Adverse events
- Major injuries due to fall
- Fall occurrence
- Device wear adherence
- Device fall alerts
- Device discrimination of serious hip-impacting vs. non-serious hip and non-hip impacting falls
- Airbag deployment
- Falls Efficacy Scale International (FES-I) short version

INTERIM ANALYSES

The study will incorporate a group sequential design (GSD) in which an interim analysis will be performed to detect an 80% protective effect of the Tango Belt at 80% power at a planned interim analysis. If a significant difference is found between the prospective Tango Belt subjects and historical controls at the interim analysis, the study will be completed early.

If not, enrollment will continue until a final sample size is reached to detect a 60% protective effect of the Tango belt at 80% power and a 5% total level of significance.

It was assumed subjects were followed for an average of 6 months, an annual fall-with-major-hip-injury rate of 15%, and sufficient historical control subjects

	to allow 1.2 allocation of subjects to treatment and central. This would require
	to allow 1:2 allocation of subjects to treatment and control. This would require
	94 subjects in the prospective Tango Belt group and 188 subjects in the
	historical control group at the interim analysis. Assuming a 30% attrition rate
	due to the fragile nature of this population, the samples sizes would increase
	to 134 and 268 in the prospective Tango Belt group and the historical control
	group, respectively. At the end of the study (should the higher effectiveness
	target not be achieved at interim analysis), 188 total subjects would be
	required in the prospective Tango Belt group and 376 subjects would be in the
	historical control group. Accounting for attrition, 268 and 536 in the
	prospective Tango Belt group and the historical control group, respectively.
FINAL ANALYSES	All final planned analyses identified in this SAP will be completed after the last
	subject has completed the End of Study visit and data entry has been finalized
	for all subjects used for analysis (including historical control subjects).

3 STUDY OBJECTIVES AND ENDPOINTS

3.1 STUDY OBJECTIVE

The current comparative clinical study is intended to establish the safety and effectiveness of the Tango Belt as an adjunctive intervention to the standard-of-care (SOC) to mitigate major hip injuries due to falls in an older adult population at-risk for fall injury.

3.1.1 PRIMARY OBJECTIVE

To assess the performance of the Tango Belt to mitigate fall-related major hip injuries in an adult population at-risk of fall injury as compared SOC only.

3.1.2 SECONDARY OBJECTIVE

To assess the performance of the Tango Belt to mitigate falls resulting in: (1) hip fractures, (2) emergency department (ED) visits or (3) hospitalizations.

3.2 STUDY ENDPOINTS

3.2.1 PRIMARY ENDPOINT

The study's **primary effectiveness endpoint** is the proportion of major hip injuries due to fall in the subjects receiving SOC as compared to subjects receiving SOC plus the Tango Belt, as reported between enrollment and the 180-day visit.

There is no primary safety endpoint for this study. Safety of the device will be determined by analysis of adverse events as an ancillary endpoint.

3.2.2 SECONDARY ENDPOINTS

The study's secondary endpoints include the proportion of each of the following:

- Hip fractures due to fall in the subjects receiving SOC as compared to subjects receiving SOC plus the Tango Belt.
- Emergency Department (ED) visits due to fall in the subjects receiving SOC as compared to subjects receiving SOC plus the Tango Belt.
- Hospitalizations due to fall in the subjects receiving SOC as compared to subjects receiving SOC plus the Tango Belt.

The secondary endpoints will be assessed using data reported between enrollment and the 180-day visit.

3.2.3 ANCILLARY ENDPOINTS

Ancillary endpoints will include:

- Adverse events
- Major injuries due to fall
- Fall occurrence
- Device wear adherence
- Device fall alerts
- Device discrimination of serious hip-impacting vs. non-serious hip and non-hip impacting falls
- Airbag deployment
- Falls Efficacy Scale International (FES-I) short version

4 SAMPLE SIZE

It is estimated that the sample size will include up to 268 subjects in the intervention group and up to 536 subjects in the historical control group. This estimated sample size includes the minimum sample size required to assess the primary endpoint with an additional 30% increase to account for possible subject attrition.

The sample size for the primary hypothesis will be calculated with 80% power. The annual rate of falls with major hip injury has been estimated between 6% and 10% in higher-risk populations within long-term care facilities. Since the fall rate is not exactly known in the study population, the fall rate observed in the historical control group, a nuisance parameter, will be used for sample size calculations. After roughly 70% of subjects were enrolled into the historical control group, the proportion of subjects who experienced a major hip injury due to a fall was calculated to be 15% and this rate was used in the sample size calculation.

The following steps were used to calculate the sample size (for further details, see section 10.1 of the Protocol):

1. Test the historical control time periods to determine if all the time periods can be used, depending on if any time periods differ in fall rate

- 2. From the remaining historical control data, the fall rate was calculated and the total sample size available for the historical control group
- 3. The sample sizes for the historical controls and the prospective Tango Belt arm at the interim analysis was calculated.
- 4. The sample size for the prospective Tango Belt arm at the final analysis was calculated using the total sample of historical controls.

This sample size determination was made based on the following specifications:

Primary Effectiveness Endpoint Assumptions:

The following assumptions were made for estimating sample size for the primary effectiveness endpoint:

- 1. Alpha of 0.025 (one-sided)
- 2. 80% power
- 3. Groups are independent

Based on the above assumptions, the minimum sample required for the intervention group for evaluation of effectiveness (unadjusted) is 94 subjects. At least 134 subjects will be enrolled to the intervention group to account for subject attrition and missing data (estimated to be 30%).

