Intervention group: The investigator or designee will review the site's EMR database to determine their current long-term care patient population's initial eligibility for meeting all study inclusion and exclusion criteria, except for waist circumference, informed consent, and ability to comply. Subjects meeting initial eligibility will then have their waist circumference obtained, and those that meet inclusion criteria will then be offered the opportunity to participate in the study through the informed consent process utilizing IRB approved subject facing recruitment materials including a video introduction of the device, a flyer on the device and research study and verbal explanation of the study with access to study site investigator for addressing questions and/or concerns. If the subject agrees to be a participant in the study, the subject will be given a written informed consent to read, sign and date (Appendix 1 - Informed Consent). If the subject has a Legally Authorized Representative (LAR) or Person of Authority (POA) in place, the POA will receive notification regarding the eligibility for the subject to participate in the study with the IRB approved subject facing recruitment materials including video introduction of the device, a flyer on the device and research study and verbal explanation of the study with access to study site investigator for addressing questions and/or concerns with the written informed consent. The POA may offer consent verbally over the phone to the investigator/ designee with notation on the Informed Consent Form and subsequent receival of copy of the ICF via USPS or email. The ICF can also be signed electronically with a provided eSignature option to the POA. All subjects or POAs will be given the opportunity to discuss the technology, risks, potential benefits, alternative therapies, and the study requirements with the investigator prior to signing the informed consent. Subjects or their POAs that provide written or electronic consent will be preliminarily enrolled into the intervention group.

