4.1 INTERIM ANALYSES

The study will incorporate a group sequential design (GSD) in which an interim analysis will be performed to detect an 80% protective effect of the Tango Belt at 80% power. If a significant difference is found between the prospective Tango Belt subjects and historical controls at the interim analysis, the study will be stopped, and the Tango Belt deemed superior to SOC alone. If not, sample size reestimation will be completed, and enrollment will continue until a final sample size is reached to detect a 60% protective effect of the Tango Belt at 80% power and a 5% total level of significance.

Following the steps from section 4, we assumed subjects were followed for an average of 6 months, an annual fall-with-major-hip-injury rate of 15%, and sufficient historical control subjects to allow 1:2 allocation of subjects to treatment and control. This would require 134 subjects in the prospective Tango Belt group and 268 subjects in the historical control group at the interim analysis using the Pocock alpha-spending function as well as accounting for 30% attrition. At the end of the study (should the higher effectiveness target not be achieved at interim analysis), 268 total subjects would be required in the prospective Tango Belt group and 536 subjects would be in the historical control group.

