5 ANALYSIS POPULATIONS

5.1 HISTORICAL CONTROL POPULATION

The Historical Control Population (HC) for this study includes retrospective subjects that meet all inclusion and exclusion criteria except for the waist circumference and need for consent. Eligible subjects' electronic health records will be mined for the baseline, midpoint, and final study metrics.

The investigator or a designee will retrospectively review the site's electronic medical record (EMR) database to determine long-term care patient population's eligibility for meeting the study inclusion criteria. The subjects in the clinical site census at the time frame 6 months prior to the IRB approval date will be screened for eligibility for study inclusion.

If there is an insufficient number of eligible subjects to meet the control group target (defined as 2 times the expected number of intervention group subjects to be enrolled from the site) at 6 months prior to the intervention group start date, the EMR database screen will extend retrospectively in 6 month increments until the control group target is reached.

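### Controls and belt subjects come from the same sites' resident records, so the assumed independence of groups is not secured, and the standard errors would be wrong if residents overlap

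*Combined protocol and SAP*

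**What the plan says.** SAP section 4 gives three assumptions for the primary endpoint: a one-sided alpha of 0.025, 80% power, and "Groups are independent".

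- **Source of controls.** SAP 5.1 and Protocol 5.3 screen the "subjects in the clinical site census at the time frame 6 months prior to the IRB approval date". If the site's control target is not met, the search moves back in 6-month steps. Protocol 10.1 says these are the sites that enrol belt subjects, and that control data may reach back to 2018.
- **Source of belt subjects.** Under Protocol 5.3 the investigator reviews the site's EMR to "determine their current long-term care patient population" and its initial eligibility.
- **Eligibility.** Controls must meet the same criteria, apart from waist circumference and consent.
- **Analysis.** SAP 7.1 matches 1:2 by nearest neighbour, without replacement, on a propensity score built from age, mobility level, sex and a fall in the past year. SAP 7.2 and 7.3 then use a logistic regression controlling for that score. No clustered, paired or robust variance is planned.

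No eligibility criterion, population definition or matching rule mentions a resident who is in both groups. The exclusion for taking part in a different investigation does not apply, because the control data belong to this study.

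**The concern.** A resident who was in a control window, survived it, stayed at the site and still meets the criteria is a candidate for the belt group. That person can then contribute two outcomes to one comparison, and the planned test treats the two as unrelated. The backward search also leaves open whether one resident may supply control records from two windows.

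Two things are at stake. The first is the standard error, and so the true error rate of the primary and secondary tests. The second is what happens if overlap is noticed late. With no stated rule, someone may delete the duplicated control records. Only residents who survived and remained eligible can be duplicated, so the deletion would depend on outcome and would affect the control group only.

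**Working it through.** **1. The plan's own figure.** The interim requirement is 94 belt subjects and 188 controls.
- Inputs from SAP 4 and 4.1: control rate 15%; 80% protective effect, so 3% on the belt; 80% power; ratio 1:2; one-sided 0.025 with Pocock spending.
- Alpha spent at half the information: 0.025 × ln(1 + (e − 1) × 0.5) = 0.0155, z = 2.157.
- Pooled rate: (0.03 + 2 × 0.15)/3 = 0.11.
- n = [2.157 × √(1.5 × 0.11 × 0.89) + 0.842 × √(0.03 × 0.97 + 0.15 × 0.85/2)]² / 0.12² = 81.5.
- With continuity correction: (81.5/4) × [1 + √(1 + 6/(81.5 × 2 × 0.12))]² = 93.5, so 94.

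The stated figure reproduces exactly, as a calculation for two independent groups. (It does so with 15% taken over the follow-up period, although SAP 4.1 calls it annual. That is a separate matter; the variance ratio in step 2 does not depend on the rate.)

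**2. Variance with overlap.** Let m residents be in both groups and ρ be the correlation of a resident's two outcomes. With a common rate p under the null and q = 1 − p:

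Var(difference) = pq(1/nT + 1/nC) − 2mρpq/(nT × nC)

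The ratio to the independent-groups variance is 1 − 2mρ/(nT + nC). The final sizes before attrition, nT = 188 and nC = 376, are in the SAP Summary. The documents give neither m nor ρ. I assume m = 94, half the belt group, and a range for ρ. The ratio is then 1 − 188ρ/564 = 1 − ρ/3, and the true size is 1 − Φ(1.96/√ratio).

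| ρ | Variance ratio | True one-sided size at nominal 0.025 |
|---|---|---|
| −0.1 | 1.033 | 0.0269 |
| 0.1 | 0.967 | 0.0231 |
| 0.3 | 0.900 | 0.0194 |

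If every belt subject overlapped (m = 188), the ratio would be 1 − 2ρ/3 and the size would run from 0.0289 (ρ = −0.1) to 0.0142 (ρ = 0.3).

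**3. Simulation of the table.** I simulated an unadjusted logistic Wald test with 15% in both groups and 94 shared residents, 400,000 runs per setting. The ordinary test rejected at 0.0246, 0.0224, 0.0206 and 0.0176 for ρ = −0.1, 0, 0.1 and 0.3. The person-clustered version rejected at 0.022 to 0.023 throughout. The ordinary test drifts with ρ as in step 2, from a starting point slightly below 0.025.

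**4. Several control records from one resident.** Here positive correlation works the other way. If 94 residents each supplied two of the 376 control records (assumption), the ratio would be 1 + ρ/6. For ρ = 0.1 and 0.3 that is 1.017 and 1.050, with sizes of 0.026 and 0.028.

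**5. Where overlap is likely.** It is most likely in the latest control window, which closes near IRB approval. As an illustration, suppose the 30% attrition also applied to controls and all 268 interim controls came from that window. Then 0.7 × 268 = 188 would still be resident, more than the 134 belt subjects sought. Waist size, consent and the run-in reduce this, and earlier windows reduce it further.

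**6. What deletion would do.** Keep the overlap at 94 of 376 (25%) and assume uninjured controls are twice as likely as injured ones to join the belt group. If a is the joining rate among the injured, 0.15a + 0.85 × 2a = 0.25, so a = 13.5%, and 27.0% for the uninjured. After deletion the control rate is 0.15 × (1 − 0.135)/0.75 = 17.3%, against 15% before.

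**The case against.** The strongest reply is that the demonstrable harm is small and mostly works against the sponsor. That stands. Risk that persists within a person gives positive correlation between groups, which makes the planned test conservative. Values near 0.3 also look high: at a 15% rate they imply a 0.15 + 0.3 × 0.85 = 40% chance of a further major hip injury in someone already injured. Overlap and correlation are both assumed.

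It is also fair that earlier control windows lower the overlap. A fall more than 12 months before belt consent meets neither the 12-month entry route nor the past-year covariate.

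A reader might infer more than the documents support:
- *That overlap occurred.* The documents report none. They only fail to prevent or detect it.
- *That the test favours the belt.* Overlap between groups does this only if the correlation is negative, and then mildly.
- *That the sample size of 94 is wrong.* It reproduces under its stated assumption, so striking that assumption would leave it without a basis.
- *That the control rate is biased upwards.* Neither document proposes deleting overlapping controls. The 17.3% shows only why the rule should be fixed beforehand.
- *That matching a belt subject to their own earlier record is an error.* Matching without replacement does not exclude it, but no bias from it has been shown. Barring it is a preference.

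**Conclusion.** The concern holds as a gap in the plan with a small effect. Independence is assumed, the recruitment scheme does not secure it, and the analysis does not allow for its failure. If residents overlap, the standard errors in SAP 7.2 and 7.3 are incorrect. With half the belt group overlapping, nominal 0.025 becomes about 0.019 to 0.023 for correlations of 0.1 to 0.3 and about 0.027 for −0.1. These sizes rest on an assumed overlap, an assumed correlation and a normal approximation without propensity adjustment. Repeated control records would push the error rate up slightly instead. The documents therefore fix no single direction, and this is a worthwhile improvement rather than a threat to the trial's conclusion.

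**What to change.** 1. Before database lock, have each site link control and belt records by resident identifier and pass on only a study-level person code. Protocol 13.4 has the databases deidentified and archived at the end of the study, so the link should be made before then.
2. Report how many residents are in both groups, before and after matching, and how many supply more than one control record. State whether the latter is allowed.
3. Use person-clustered robust standard errors in the logistic regressions of SAP 7.2 and 7.3.
4. In SAP section 4, keep the independence assumption but call it a planning approximation for the sample size only.
5. State in advance that control records of residents who later join the belt group are kept.

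The cost is SAP wording, a small programming change and an identifier link at each site. No new data collection is needed. Controls are included without consent, so the link may need IRB notification.
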